10.2.1.3 Change in depressive or (hypo)manic symptoms

Change of baseline depressive symptoms or development of (hypo)manic symptoms based on clinical review are exempt from safety reporting unless they:

- (a) are associated with self-harm
- (b) are associated with uncharacteristic erratic behaviour
- (c) meet any one or more of the seriousness criteria

These events are collected on case report forms.

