8.11 Discontinuation/withdrawal of participants from study protocol

Study participants have the right to voluntarily discontinue study treatment or withdraw from the study at any time for any reason without any consequences.

The investigator has the right to discontinue a participant from study treatment or withdraw a participant from the study at any time if it is in the best interest of the participant. In this instance, participants must discontinue the investigational medicinal product (Scopolamine) and be withdrawn from the study. Reasons for investigator to discontinue a participant from study treatment include but are not limited to:

- Pregnancy,
- Involuntary detention under the MHA 2001 in an acute psychiatric inpatient unit
- Treatment with ECT
- Severity of symptoms such that participation in a clinical trial is not appropriate because of the risk of imminent self-harm (based on review by clinician at study visit)
- Development in the study of narrow angle glaucoma, myasthenia gravis, paralytic ileus, pyloric stenosis, toxic megacolon and acute porphyria.
- Development post-infusion of bradycardia (HR < 50 bpm), tachycardia (HR > 100bpm) or hypotension (Systolic BP <90mm HG or Diastolic BP <60mm Hg) that required clinical treatment (e.g. administration of additional medications, review in Emergency Department)
- Treatment at day of infusion with anticholinergic medications (e.g. Physostigmine, Biperiden, Procyclidine)

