10.2.1.2 Scopolamine infusion related

The following events are considered expected, transient side effects of scopolamine therapy and are therefore exempt from safety reporting if they occur in the 90 minutes post IMP infusion (visit 3, visit 4 or visit 5). These events will be captured on a study outcome form.

- (a) Drowsiness
- (b) Blurred vision
- (c) Dry mouth
- (d) Thirst
- (e) Urinary retention

The above occurrences are considered Adverse events and therefore reportable if any of the following occur:

- medical intervention or treatment
- prolonged monitoring in addition to the 90 minutes post infusion required by the protocol
- deemed medically significant by an investigator
- cessation of the study drug (current or subsequent infusions)

These events must be reported as SAEs/SARs if they meet one or more of the seriousness criteria.

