10.2.1.5 Psychometric measures

Variations in psychometric assessments captured on HDRS, YMRS, CGI-S, CGI-I, VAS, MADRS, GAF and POMS are exempt from safety reporting. Psychometric assessments are collected on case report forms.

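### Stopping infusions does not make mood worsening a reportable adverse event, so non-serious worsening that ends treatment can be missing from the safety tables, and the status of self-harm risk is unclear

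*Protocol*

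**What the plan says.** Protocol 10.2 requires AEs to be reported to the sponsor, apart from events set aside as outcomes in 10.2.1. For mood, 10.2.1.3 reads: "Change of baseline depressive symptoms or development of (hypo)manic symptoms based on clinical review are exempt from safety reporting unless they" satisfy one of three conditions:

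- (a) they "are associated with self-harm";
- (b) they "are associated with uncharacteristic erratic behaviour";
- (c) they "meet any one or more of the seriousness criteria".

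It adds: "These events are collected on case report forms". Protocol 10.2.1.4 exempts psychotropic medication changes, and 10.2.1.5 does the same for rating scales: "Variations in psychometric assessments captured on HDRS, YMRS, CGI-S, CGI-I, VAS, MADRS, GAF and POMS are exempt from safety reporting". Neither lists an exception.

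Protocol 10.2.1.2 exempts five expected scopolamine effects in the 90 minutes after infusion. It makes them reportable again on any of four triggers, one of which is "cessation of the study drug (current or subsequent infusions").

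Among the reasons for an investigator to stop treatment, Protocol 8.11 lists: "Severity of symptoms such that participation in a clinical trial is not appropriate because of the risk of imminent self-harm".

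**The concern.** Safety is part of the primary objective in both documents, and the participants are depressed people with bipolar disorder. When a listed infusion effect such as thirst stops an infusion, it must be reported. When worsening mood stops the infusions, it need not be, unless one of the three conditions is met. A difference between arms in treatment stopped for mood could then be missing from the AE tables and from the safety data sent to the DSMB.

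Classification also matters outside the tables. In Protocol 8.11 the duty to arrange follow-up until an event resolves or stabilises attaches to withdrawal because of an AE.

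Separately, 8.11 treats a risk of self-harm as enough to stop treatment, while condition (a) of 10.2.1.3 does not say whether risk or ideation without an act is enough to report.

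**Working it through.** The plan gives no figure on this point, so the check is textual.

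**Step 1. What restores reporting in each exemption**

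| Protocol section | Exempt event | Investigator judges it significant | Infusions stopped | Serious | Other triggers |
|---|---|---|---|---|---|
| 10.2.1.1 | Cannulation effects | Yes | Not listed | Yes | Worse than commonly seen |
| 10.2.1.2 | Infusion effects | Yes | Yes | Yes | Intervention or treatment; monitoring beyond 90 minutes |
| 10.2.1.3 | Mood change | Not listed | Not listed | Yes | Self-harm; erratic behaviour |
| 10.2.1.4 | Psychotropic changes | None listed | None listed | None listed | None listed |
| 10.2.1.5 | Scale scores | None listed | None listed | None listed | None listed |

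Mood change has neither the cessation trigger of 10.2.1.2 nor the significance trigger of 10.2.1.1 and 10.2.1.2. A medication change or a score rise does not bring the event back either.

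**Step 2. Case A: non-serious worsening, no self-harm, no erratic behaviour; the participant asks for no more infusions and stays in follow-up.** Protocol 8.11 provides for this by inviting such participants to complete the questionnaires at the remaining treatment visits.

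- AE form: not required under 10.2.1.3.
- SAP 14.2 (AEs, action taken) and SAP 14.3 (SAEs): absent.
- SAP 14.3.1 (withdrawals with reason): counts people withdrawn from the study, so absent.
- SAP 12.4 and 14.1 (infusions received, full dose achieved): visible as missed infusions, with no reason.
- SAP 14.3.3: plans no further AE analysis.
- Efficacy (SAP 5.2.2): enters mean change on the depression and global scales. Depressive worsening has no incidence endpoint of its own, whereas (hypo)mania has one (YMRS above 6).

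**Step 3. Case B: the same worsening, but the investigator stops treatment.** Protocol 8.11 then has the participant withdrawn from the study, so the case should appear with its reason in SAP 14.3.1. It should also appear in the between-group summary of drop-out reasons promised in Protocol 11.1. It is still not an AE. SAP 14.3.1 does not state a split by arm, although 14.2, 14.3 and 14.3.2 do.

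**Step 4. Case C: treatment stopped for risk of imminent self-harm, with no act.** Condition (a) can be read to include or exclude risk. Through condition (c), the medically important criterion in Protocol 10.1.3 covers events that may jeopardise the participant or need intervention to prevent a serious outcome, and this may capture the case. An inpatient admission is serious outright. Two investigators could classify the same case differently.

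**Step 5. Scale.** One participant is 1/25 = 4% of an arm. Purely as illustration, 3 versus 0 would be 3/25 = 12% versus 0%, and if all three were Case A the AE tables could show 0 versus 0. The documents give no expected count, and the share captured as medically important cannot be derived from them.

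**The case against.** Depressive symptoms are the efficacy outcome, and Protocol 10.2 sets outcomes aside on purpose. Keeping routine fluctuation of the disease under study out of AE reporting is a defensible choice. The SAP compares the arms on HDRS, MADRS, CGI, psychiatric admission for depression, new or increased antidepressant and YMRS above 6. Protocol 10.5 also lets the DSMB review outcome data. All of this stands, and it is why the problem is one of classification rather than lost data. It does not explain why cessation restores reporting in 10.2.1.2 and not in 10.2.1.3. Nor does it fully settle the DSMB point, because SAP 8.1 confines interim analyses to safety data.

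A second objection is that 10.2.1.2 covers a short list of expected drug effects over 90 minutes, while 10.2.1.3 covers the disease over the whole trial, so identical triggers should not be expected. This stands in part. The judged-significance trigger overlaps with the medically important criterion that condition (c) already brings in. Cessation is the main trigger that is truly absent.

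A reader might go further and infer that a participant stopped for self-harm risk is exempt and drops out of the safety record. The documents do not support that. Such a case can fall under condition (a) or the medically important criterion, and if the investigator stops treatment it should reach the withdrawal table with a reason.

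**Conclusion.** The point holds for non-serious mood worsening that ends infusions without self-harm or erratic behaviour. Such an event need not be an AE and can be absent from SAP 14.2. If the participant remains in follow-up, no planned table gives the reason for stopping. For self-harm risk, the finding is an ambiguity between Protocol 8.11, 10.1.3 and 10.2.1.3, not an exemption.

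The size cannot be estimated from the documents; the only firm figure is 4 percentage points per participant per arm of 25. The primary efficacy analysis is unaffected. The correction is worth making because safety is in the primary objective and small counts matter at this sample size.

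The conclusion assumes that the SAP's AE tables are built from reported AEs, and that withdrawal in SAP 14.3.1 means leaving the study, as its text says. The case report forms were not available, so whether they record a reason for each missed infusion is unknown.

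**What to change.** Reconcile Protocol 8.11, 10.2.1.2 and 10.2.1.3 on reporting:

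1. In 10.2.1.3, make mood change that leads to cessation of the current or later infusions a reportable AE.
2. State whether suicidal ideation, or a judged risk of self-harm without an act, falls under condition (a).
3. In SAP 14, add a table by arm of participants who stopped infusions, with the reason (mood worsening and self-harm risk as separate categories), whether or not they left the study. Include it in the DSMB safety data under the trial's masking arrangements.

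The other 10.2.1.2 triggers should not simply be copied across. Prolonged monitoring there refers to the 90 minutes after infusion and has no clear meaning for mood between visits. Intervention or treatment would cut across the exemption in 10.2.1.4 and duplicate the antidepressant endpoint (SAP 5.2.2, item 12).

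The cost is two changes to protocol wording, a few extra AE forms and one table. If an amendment is no longer practical, the table alone could still be produced, provided the reason for stopping was recorded. These changes concern reporting and analysis only; they leave the criteria for stopping treatment as they are.

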10.2.1.4 Psychotropic medications

Changes in psychotropic medications are exempt from safety reporting. These changes are collected on case report forms.

10.2.1.5 Psychometric measures

Variations in psychometric assessments captured on HDRS, YMRS, CGI-S, CGI-I, VAS, MADRS, GAF and POMS are exempt from safety reporting. Psychometric assessments are collected on case report forms.

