10.1.3 Serious Adverse Event (SAE) or Serious Adverse Reaction (SAR)

Any untoward medical occurrence or affect that at any dose meets one or more of the following criteria:

- results in death,
- is life-threatening*,
- requires hospitalisation (defined as >24 hour hospital stay or admission to inpatient hospital area) or prolongation of existing hospitalisation,
- results in persistent or significant disability or incapacity,
- is a congenital anomaly or birth defect
- is medically important**

* This refers to an event in which the participant was at risk of death at the time of the event; it does not refer to an event which hypothetically might have caused death if it were more severe.

** Some medical events may jeopardise the participant or may require an intervention to prevent one of the above characteristics/consequences. Such events (hereinafter referred to as 'important medical events') should also be considered as 'serious' in accordance with the definition.

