## 14 Safety Analyses

The results of clinical monitoring including blood pressure or heart rate changes, and AEs secondary to phlebotomy or cannulation will be examined between the groups. Adverse events will be coded according to the Medical Dictionary for Regulatory Activities (MedDRA). The incidence of treatment-emergent adverse events will be summarized by system organ class (SOC) and preferred term.

Safety data will be presented primarily in a descriptive fashion. The small sample size and likely low adverse event rates will mean any inference is likely underpowered to detect a range of meaningful differences.

Blinded data will be presented to the DSMB for safety evaluation to coincide with scheduled DSMB meetings.

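### Non-serious suicidal ideation without self-harm or erratic behaviour falls outside AE reporting, and SAP 14 plans no by-arm summary that isolates it

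*Protocol*

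**What the plan says.** Two clauses in Protocol 10.2.1 take changes in depressive state out of safety reporting.

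- Section 10.2.1.3: "Change of baseline depressive symptoms or development of (hypo)manic symptoms based on clinical review are exempt from safety reporting unless they" meet one of three conditions: (a) they "are associated with self-harm", (b) they "are associated with uncharacteristic erratic behaviour", or (c) they "meet any one or more of the seriousness criteria".
- Section 10.2.1.5: "Variations in psychometric assessments captured on HDRS, YMRS, CGI-S, CGI-I, VAS, MADRS, GAF and POMS are exempt from safety reporting". This clause carries no exceptions.

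Both sections add that the data are still collected on case report forms.

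Elsewhere the protocol treats self-harm risk as a recognised hazard. It is exclusion criterion 10, and Protocol 8.11 lists as a reason for discontinuation "Severity of symptoms such that participation in a clinical trial is not appropriate because of the risk of imminent self-harm". Safety is part of the primary objective (Protocol 7.1, SAP 5.1.1).

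SAP 14 opens with: "The results of clinical monitoring including blood pressure or heart rate changes, and AEs secondary to phlebotomy or cannulation will be examined between the groups". Its subsections cover exposure, adverse events, SAEs, withdrawals, deaths, pregnancies, laboratory tests, vital signs and ECG. SAP 14.3.3 and SAP 15 plan nothing further. Apart from recorded variables, SAP 5.3 provides only for change scores. Neither document mentions suicidal ideation by name.

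**The concern.** The trial tests a putative rapid-acting antidepressant in bipolar depression. Whether suicidal ideation emerges or worsens more often on drug or on placebo is a question its safety report would be expected to address. Raters complete the HDRS at Visits 1 to 7 and the MADRS at Visits 2 to 7, so depressive state is observed repeatedly after randomisation. The analysis plan then uses those ratings only as efficacy outcomes, through totals and response or remission categories. A total can fall because other symptoms improve while one symptom gets worse, so an efficacy result on the total does not settle the safety question.

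The two exemption clauses also do not match. If a change in a rating reflects ideation, 10.2.1.3 asks whether an exception applies, whereas 10.2.1.5 exempts the change outright. The documents do not say which clause governs.

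**Working it through.** The plan states no figure on this point, so the check is mainly a reading of the clauses side by side.

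**Step 1. Which ideation is reportable?** Under 10.2.1.3, ideation is reportable if any of (a), (b) or (c) applies. Condition (c) leads to Protocol 10.1.3, where seriousness includes hospitalisation, threat to life and medically important events: "Some medical events may jeopardise the participant or may require an intervention to prevent one of the above characteristics/consequences". Two of the three conditions, (b) and (c), need no act of self-harm. What remains exempt is ideation that is non-serious, without self-harm and without uncharacteristic erratic behaviour.

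**Step 2. Where could ideation appear in the planned output?**

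| Route | What it catches | Isolates ideation? |
|---|---|---|
| SAEs by treatment group (SAP 14.3) | Cases meeting a seriousness criterion | No dedicated row; severe end only |
| Withdrawals with reason (SAP 14.3.1) | Cases leading to withdrawal | No; no by-arm split stated there |
| Drop-out reasons between groups (Protocol 11.1) | Same, by group | No |
| Psychiatric admission for depression (secondary endpoint 11) | Cases admitted | No |
| New or increased antidepressant (secondary endpoint 12) | Cases with a treatment change | No |
| Participant-reported effects and PRISE (secondary endpoint 15) | What participants volunteer; PRISE is optional | No; no mood or suicidality domain is named |
| HDRS and MADRS change by arm (SAP 5.2.2, 13.1, 13.2) | Overall severity | No; no item-level analysis |

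**Step 3. Are other exempt categories treated the same way?** No. (Hypo)manic symptoms are exempt but return as secondary endpoint 14 (YMRS above 6). Psychotropic changes are exempt, but antidepressant starts and dose increases return as endpoint 12. The expected infusion effects in 10.2.1.2 are exempt but go on a study outcome form and are taken up in SAP 14.1. Non-serious ideation has no such counterpart.

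**Step 4. What could a by-arm table show with 25 per arm?** The rates below are assumptions for illustration; the documents give none.

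- Chance of at least one case in an arm, 1 − (1 − p)^25: 0.72 for p = 5%, 0.93 for p = 10%, 0.996 for p = 20%.
- Upper 95% limit after 0 of 25: one-sided 1 − 0.05^(1/25) = 11.3%; two-sided 1 − 0.025^(1/25) = 13.7%.
- Power of a two-sided Fisher test at 0.05: 0.20 for 5% against 20%, 0.30 for 10% against 30%, 0.55 for 5% against 30%.

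Such a table would usually reveal that cases occurred, and would bound the rate if none did. It could not support a test between arms.

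**The case against.** A reader might infer that all suicidal ideation without self-harm is exempt and that a difference between arms would be reported nowhere. The documents do not support that. Conditions (b) and (c) of 10.2.1.3, with the medically important criterion, make some such ideation reportable. SAEs are tabulated by treatment group, and imminent self-harm risk without any act is a listed reason for discontinuation, so severe cases have several routes into the report. This part of the objection stands and limits the point to the non-serious remainder.

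Three further arguments deserve weight.

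- The exemption governs reporting, not data capture, and the scales stay on the case report forms. That is correct. The gap is therefore in the analysis plan and in the mismatch between the two clauses, and the exemption for routine score changes need not be removed.
- The documents describe the HDRS only as a 21-item scale and the MADRS as a 10-item scale. They list no suicidality item and do not show that item scores are stored. That also stands, and it makes the table conditional.
- Numbers will be small, participants at imminent risk are excluded at entry, and SAP 14 already concedes that safety inference is underpowered. That rules out a test. It does not rule out a descriptive display, which is how SAP 14 presents safety data anyway.

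**Conclusion.** The point holds in a limited form. If the plan is followed as written, non-serious emergent or worsening ideation, without self-harm or erratic behaviour, is outside AE reporting and has no by-arm summary. The stronger reading, that ideation is exempt without condition and invisible in the results, should not be drawn.

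The size cannot be put as a number of events, because neither document gives a rate, and a count of completed rating forms would not measure it. What is affected is one category of safety event across both arms of the 50 participants to be randomised. The primary efficacy analysis is untouched.

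The conclusion on the gap assumes that investigators would handle such ideation as a symptom or score change, which the two clauses invite. The proposed table further assumes that the forms contain a suicidality item and that item scores are retained. If that second assumption fails, the gap remains but this table cannot fill it.

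**What to change.** 1. Reconcile Protocol 10.2.1.3 with 10.2.1.5, so that the documents state which clause governs when a score change reflects suicidal ideation. The choice is for the sponsor and investigators. The exemption for routine score changes can stay.
2. Confirm whether the HDRS and MADRS forms in use contain a suicidality item, and whether item scores are in the database or only on the questionnaires.
3. If so, add one descriptive table to SAP 14, by arm: the shift in each item from Visit 3 to the worst score at Visits 4 to 7, and the number and percentage with any increase from Visit 3. State that no test will be made.
4. Give the same table to the DSMB by masked arm. Protocol 10.5 and SAP 8.1 already provide for DSMB review of interim safety data, with an independent statistician.
5. If item scores do not exist, say in the SAP that emergent ideation cannot be summarised separately.

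Cost: one table if item scores are in the database, with no new assessment. If only totals were entered, the item scores must be keyed from existing questionnaires: at most 50 participants × 2 scales × 5 visits (3 to 7) = 500 forms. The drawback is a small-number comparison that readers may over-interpret, so the descriptive label matters.

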10.2.2 Assessment of seriousness

An appropriately qualified, delegated member of the site team should make an assessment of seriousness as defined in section 10.1.3.

10.2.3 Assessment of causality

All adverse events judged by either the investigator or the sponsor as having a reasonable suspected causal relationship to an investigational medicinal product qualify as adverse reactions.

The investigator must make an assessment of whether the AE/SAE is likely to be related to treatment according to the following definitions:

- Unrelated: Where an event is not considered to be related to the study medication.
- Unlikely: where a temporal relationship to the study medication makes a relationship improbable (but not impossible) and disease or other drugs provide plausible explanations.
- Possible: Although a relationship to the study medication cannot be completely ruled out, the nature of the event, the underlying disease, concomitant medication or temporal relationship make other explanations possible.
- Probable: The temporal relationship and absence of a more likely explanation suggest the event could be related to the study medication.
- Definite: Plausible temporal relationship and cannot be explained by disease or other drugs.

All AEs/SAEs judged as having a reasonable suspected causal relationship (e.g. definite, possible, probable) to the study medication will be considered as ARs/SARs.

All AEs/SAEs judged as being related (e.g. possibly, probably) to an interaction between the study medication and another medication will also be considered to be ARs/SAR.

The causality assessment provided by the investigator will also be reviewed by the sponsor. The investigator causality assessment should not be downgraded by the sponsor.

Alternative causes such as natural history of the underlying disease, concomitant therapy, other risk factors and the temporal relationship of the event to the treatment should be considered.

